4. PARTICIPANT ENTRY

4.1. PRE-REGISTRATION EVALUATIONS

Participants do not need any pre-registration evaluations before being considered for recruitment. Parent / guardian must be able to give informed consent to participate in the study.

Child and accompanying parent / guardian are contactable by telephone and able to attend 3 monthly visits, which will be scheduled at the same time as their existing clinic appointment.

Child and parent/guardian are able to comply with the requirements and restrictions listed in the consent form.

4.2. INCLUSION and EXCLUSION CRITERIA

Table 2: Inclusion and Exclusion criteria for each aim

Aims	Inclusion Criteria	Exclusion Criteria
Aim 1	Children aged 1-5 years, undergoing clinically indicated flexible bronchoscopy, for recurrent preschool wheeze, as determined by their existing clinical team as part of their routine medical management	Children with a known alternative respiratory diagnosis such as cystic fibrosis or bronchiectasis. A child will not be eligible for inclusion in this study if following medical assessment, physical examination or initial investigations, the physician
Aim 2	Children aged 1-5 years attending the paediatric respiratory clinics at the Royal Brompton Hospital with either (i) $>/=2$ hospitalisations for acute wheeze; and/or	
Aim 3		

(ii) at least 1 admission requiring high dependency unit or intravenous bronchodilator therapy; during the previous year.	considers the child to be unfit for the study.
---	--

Withdrawal criteria: If the person with parental responsibility loses capacity, the child will be withdrawn from the study. Any identifiable data or tissue already collected with consent will be retained and used for the study, but no further data collection or procedures would be undertaken.

5. ADVERSE EVENTS

5.1. DEFINITIONS

Adverse Event (AE): any untoward medical occurrence in a patient or clinical study subject.

Serious Adverse Event (SAE): any untoward medical occurrence or effect that:

- **Results in death**
- **Is life-threatening** – refers to an event in which the subject was at risk of death at the time of the event; it does not refer to an event which hypothetically might have caused death if it were more severe
- **Requires hospitalisation, or prolongation of existing inpatients' hospitalisation**
- **Results in persistent or significant disability or incapacity**
- **Is a congenital anomaly or birth defect**

Medical judgement should be exercised in deciding whether an AE is serious in other situations. Important AEs that are not immediately life-threatening or do not result in death or hospitalisation but may jeopardise the subject or may require intervention to prevent one of the other outcomes listed in the definition above, should also be considered serious.

5.2. REPORTING PROCEDURES

All adverse events should be reported. Depending on the nature of the event the reporting procedures below should be followed. Any questions concerning adverse event reporting should be directed to the Chief Investigator in the first instance.

5.3.1 Non serious AEs

All such events, whether expected or not, should be recorded

5.3.2 Serious AEs

An SAE form should be completed and emailed to the Chief Investigator within 24 hours. However, relapse and death due to preschool wheeze, and hospitalisations for elective treatment of a pre-existing condition do not need reporting as SAEs.

All SAEs should be reported to the <name of REC> where in the opinion of the Chief Investigator, the event was:

- 'related', ie resulted from the administration of any of the research procedures; and

- 'unexpected', ie an event that is not listed in the protocol as an expected occurrence

Reports of related and unexpected SAEs should be submitted within 15 days of the Chief Investigator becoming aware of the event, using the NRES SAE form for non-IMP studies. The Chief Investigator must also notify the Sponsor of all related and unexpected SAEs.

Local investigators should report any SAEs as required by their Local Research Ethics Committee, Sponsor and/or Research & Development Office.

Contact details for reporting SAEs

[contact]

[name]

[contact]

[contact], attention [name]

Please send SAE forms to: [name]

[contact] (Mon to Fri 09.00 – 17.00)

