Physical Examination	X	X	X	X	X
Medical History	X	X	X	X	X
Informed consent	X	X	X	X	X
Validated symptom questionnaire (TRACK)	X	X	X	X	X
Paediatric Asthma Caregivers Quality of Life Questionnaire: PACQLQ	X	X	X	X	X
Forced oscillation technique and bronchodilator reversibility test	X	X	X	X	X
Oropharyngeal and nasal swabs for pathogen specific PCR to detect Moraxella/Streptococcus/Haemophilus	X		X		X
Skin prick test (house dust mite, cat, dog, grass, tree pollen, and mixed moulds)	X				
Sputum induction for bacterial culture and pathogen specific PCR to detect Moraxella/Streptococcus/Haemophilus	X				X
Blood sample collection (finger prick) for point of care testing and laboratory studies	X	X	X	X	X

Children participating in Aim 3 only: Our experience is that intervention studies are challenging in preschool wheezers. Parents are often hesitant about proposed changes to treatment, even though existing treatment may be ineffective, and they may not adhere to prescribed therapy. Aim 3 is to undertake a proof-of-concept feasibility study for using biomarker results to determine management. Children in this Aim will be recruited from the cohort of children in Aim 2, and therefore

will have all the tests carried out at the same intervals. If parents consent to taking part, children will have the following treatment adjustments based on the results of their tests (Table 5):

Table 5: Proposed biomarker guided management for proof-of-concept feasibility study

Biomarker result at baseline assessment	Treatment
Allergen sensitisation +/- blood eosinophilia ($\geq 0.3 \times 10^9/L$)	Regular inhaled corticosteroids
Non-atopic*; positive bacterial detection in sputum	4 weeks of targeted antibiotics
Non-atopic*; negative bacterial infection	Short acting bronchodilators as required

*non-atopic is defined as blood eosinophil of $<0.3 \times 10^9/L$ + no evidence of allergen sensitisation

This proof-of-concept study will be undertaken to understand whether parents will agree to their children taking part in an interventional trial, and to assess the feasibility of the proposed targeted treatment approach in a subgroup of wheezers. Wheeze attacks and symptoms over the course of a year will be compared to the children in Aim 2 as a reference control cohort. This aim will enable a more accurate sample size calculation and design for a future interventional trial.

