8.2. CONSENT

Consent to enter the study must be sought from each participant's parents or care giver (with parental rights) only after a full explanation has been given, an information leaflet offered and time allowed for consideration. Signed participant consent should be obtained. The right of the participant to refuse to participate without giving reasons must be respected. After the participant has entered the study the clinician remains free to give alternative treatment to that specified in the protocol at any stage if he/she feels it is in the participant's best interest, but the reasons for doing so should be recorded. In these cases the participants remain within the study for the purposes of follow-up and data analysis. All participants are free to withdraw at any time from the protocol treatment without giving reasons and without prejudicing further treatment.

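### Section 5.3.2 exempts deaths due to preschool wheeze from SAE reporting with no exception for Aim 3, where the protocol itself adjusts wheeze treatment

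*Combined protocol and SAP*

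**What the plan says.** Section 5.1 defines a serious adverse event by outcome. One criterion is "Results in death", with no cause of death excluded. Section 5.2 asks for all adverse events to be reported and points to the procedures that follow it.

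Section 5.3.2 sets the serious route: "An SAE form should be completed and emailed to the Chief Investigator within 24 hours". It then makes an exception: "relapse and death due to preschool wheeze, and hospitalisations for elective treatment of a pre-existing condition do not need reporting as SAEs". Onward reporting to the REC applies to SAEs that the Chief Investigator considers both unexpected and related, where related means that the event "resulted from the administration of any of the research procedures". For the Sponsor, "The Chief Investigator must also notify the Sponsor of all related and unexpected SAEs". The section also says: "Local investigators should report any SAEs as required by their Local Research Ethics Committee, Sponsor and/or Research & Development Office".

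Section 6 describes Aim 3. If parents consent, "children will have the following treatment adjustments based on the results of their tests", as set out in Table 5. Section 8.2 confirms that the protocol specifies treatment, since it says that "the clinician remains free to give alternative treatment to that specified in the protocol" and asks for the reasons to be recorded.

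**The concern.** An exemption for events of the underlying disease is familiar in observational work, where the study does nothing that could change the course of the disease. Aim 3 is different, because the study directs a change in wheeze treatment. A fatal wheeze attack after such a change is the event most relevant to the safety of the intervention, and it is one of the events the protocol says need not be reported as an SAE.

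The order of the steps matters. The SAE form is the stated means of bringing an event to the Chief Investigator. The exemption applies once a death has been attributed to wheeze, and the protocol neither names who makes that attribution nor asks whether the treatment change contributed. The question of relatedness may therefore never be put. What is at stake is patient safety; no study estimate depends on it.

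**Working it through.** The plan gives no figure to reproduce. The check compares the passages and then counts who is affected.

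**1. Is a wheeze death an SAE?** By section 5.1, yes: death is a criterion and no cause is excluded. By section 5.3.2, it need not be reported as one. The two sections are not reconciled.

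**2. Does the exemption reach Aim 3?** It names no aim, and section 5 is the only adverse-event section, with no aim-specific rule. Neither the Aim 3 text in sections 3 and 6 nor section 8.2 restores reporting. That the exemption covers every aim is an inference from its study-wide wording.

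**3. Does another route catch an exempt death?**

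| Possible route | What it provides | Does it close the gap? |
|---|---|---|
| Section 5.2, general duty to report | Refers to the procedures below it | No. Those procedures give no route for an exempt serious event |
| Section 5.3.1 | Recording of non-serious events | No. A death is not a non-serious event |
| Section 5.3.2, REC paragraph | Starts from all SAEs and turns on the Chief Investigator's opinion | Not clearly. It does not say how an event without a form reaches that opinion |
| Section 5.3.2, local investigators | Reporting as the local REC, Sponsor or R&D Office requires | Not clearly. Those requirements are not in the documents, and the sentence does not override the exemption |
| Sections 2, 3.1 and 6, outcome data | Wheeze attacks, symptoms, unscheduled visits | No. Study visits are 3-monthly, and there is no expedited step |
| Safety or data monitoring committee | None described in the supplied text | No |

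**4. Would a reported death meet the test for onward notification?** The definition of related refers to research procedures. The text does not say whether a Table 5 treatment adjustment is one. Even a death that reached the Chief Investigator could therefore be judged against wording that does not clearly include the intervention.

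**5. How many children?** Aim 3 has a target of 15 children, and each child is followed for 12 months (section 3).

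Aim 3 follow-up = 15 children × 1 year = 15 child-years.

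This is an upper bound on exposure to adjusted treatment. One row of Table 5 is a 4-week course, a child may already be on the assigned treatment, and the figure assumes full recruitment and no dropout. The documents give no death rate, so no expected number of deaths is calculated.

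**The case against.** The strongest reply is that the exemption is narrower than it looks. It says that wheeze deaths need not be reported as SAEs; it does not say that they go unreported, and section 5.2 still asks for every adverse event to be reported. The wording is permissive. The REC paragraph does not make the Chief Investigator's opinion conditional on a form, and a death attributed to a research procedure arguably falls outside a clause about deaths due to wheeze. At a single centre the Chief Investigator would probably learn of a death anyway. Wheeze attacks are already a study outcome, which makes the exemption a defensible choice for the observational aims.

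Much of this stands, and it limits the point. A reader might infer that a wheeze death in Aim 3 vanishes from the study, or that it can never reach the relatedness judgement. The documents do not support that, because section 5.2 and the REC paragraph leave an opening. A reader might also infer that the exemption is wrong in every aim. That does not follow either, since Aims 1 and 2 direct no treatment change.

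The opening is nevertheless not a procedure. Section 5 gives an exempt death no form, no deadline and no named person to decide whether it is exempt. Relying on word of mouth at one centre does not replace a written rule for the gravest event.

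The undefined term for relapse is a secondary matter. Only elective hospitalisations are expressly exempt, so the status of an emergency wheeze admission is unclear. The text does not establish that such admissions are exempt.

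**Conclusion.** The point holds for Aim 3 and should be fixed before that aim proceeds. Following section 5.3.2 as written, a wheeze death after a study-directed treatment change may skip the 24-hour form. No clear route then leads to the Chief Investigator's assessment or to REC and Sponsor notification. Sections 5.1, 5.2 and 5.3.2 do not agree with one another or with the Aim 3 text.

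The scope is small: at most 15 children and at most 15 child-years. The importance rests on the consequence of a single event, because no frequency can be derived from the documents. The conclusion assumes that section 5 applies to all aims, as its unrestricted wording implies, and that no reporting requirement outside the documents overrides the exemption. SAEs outside the exemption, including non-wheeze deaths, remain reportable. This is a finding about event reporting and implies no view on the treatments in Table 5.

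**What to change.** Reconcile sections 5.1, 5.2 and 5.3.2 with the Aim 3 text in section 6:

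1. Remove death from the exemption in section 5.3.2, at least for children in Aim 3.
2. State that, for REC and Sponsor reporting, related events include those that may result from a protocol-directed treatment adjustment as well as from a research procedure.

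As secondary clarifications, define relapse and say whether an emergency wheeze admission in Aim 3 is reportable as an SAE.

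The cost is a wording amendment to one section. The added load from the change on deaths is one SAE form per wheeze death in Aim 3, expected to be close to zero. Under the minimum version the exemption stays as it is for children outside Aim 3. If emergency wheeze admissions were made reportable, the load would be larger and would need its own estimate, because eligibility rests on recent admissions and the documents give no admission rate for the follow-up year.

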6. ASSESSMENT AND FOLLOW-UP

Children participating in Aim 1: One-off assessment carried out on the day of the bronchoscopy and no follow-up needed. Assessments carried out are listed below in Table 4. We will aim to do the oropharyngeal swab, skin prick testing (if not done in the last 6 months) and finger prick blood test under general anaesthetic, during the bronchoscopy procedure.

A bronchoscopic programme which enables research samples to be collected, with parental informed consent, from children undergoing clinically indicated bronchoscopy for severe recurrent wheeze is established at the Royal Brompton Hospital. The [name] group have shown that it is safe to take additional samples and this does not add significant time.

Table 3: Assessments and investigations for Aim 1 only:

Assessments/ Investigations	Study visit
Vital Signs measurements (Temp, BP, Pulse and respiration)	X
Height and weight	X
Physical Examination	X
Medical History	X
Informed consent	X
Validated symptom questionnaire (TRACK)	X
Paediatric Asthma Caregivers Quality of Life Questionnaire: PACQLQ	X
Forced oscillation technique and bronchodilator reversibility test	X
Oropharyngeal and nasal swabs for pathogen specific PCR to detect Moraxella/Streptococcus/Haemophilus	X
Skin prick test or blood aeroallergen IgE (house dust mite, cat, dog, grass, tree pollen and mixed moulds)	X

Sputum induction for bacterial culture and pathogen specific PCR to detect Moraxella/Streptococcus/Haemophilus	X
Blood sample collection (Finger prick) for point of care testing and laboratory studies	X
Bronchoscopy – bronchoalveolar lavage and endobronchial biopsy (part of routine clinical management and surplus sample used for study with parental consent)	X

Children participating in Aim 2 and Aim 3: Children in these two aims do **not** need bronchoscopy. They will have the panel of non-invasive tests listed in Table 5, at the intervals below. These children will be seen for the research study at the same time as their routine outpatient clinic follow-up visits, which will be every three months over one year (Visits 1-4), and therefore no separate research visits are required. The tests listed below in Table 5 will be undertaken at the times indicated.

Table 4: Assessments and Investigations for Aims 2 and 3.

Assessments/ Investigations	Study visits (every 3 months for 12 months)				
	Baseline	1	2	3	4
Vital Signs measurements (Temp, BP, Pulse and respiration)	X	X	X	X	X
Height and weight	X	X	X	X	X
Physical Examination	X	X	X	X	X
Medical History	X	X	X	X	X
Informed consent	X	X	X	X	X
Validated symptom questionnaire (TRACK)	X	X	X	X	X
Paediatric Asthma Caregivers Quality of Life Questionnaire: PACQLQ	X	X	X	X	X
Forced oscillation technique and bronchodilator reversibility test	X	X	X	X	X
Oropharyngeal and nasal swabs for pathogen specific PCR to detect Moraxella/Streptococcus/Haemophilus	X		X		X
Skin prick test (house dust mite, cat, dog, grass, tree pollen, and mixed moulds)	X				
Sputum induction for bacterial culture and pathogen specific PCR to detect Moraxella/Streptococcus/Haemophilus	X				X
Blood sample collection (finger prick) for point of care testing and laboratory studies	X	X	X	X	X

Children participating in Aim 3 only: Our experience is that intervention studies are challenging in preschool wheezers. Parents are often hesitant about proposed changes to treatment, even though existing treatment may be ineffective, and they may not adhere to prescribed therapy. Aim 3 is to undertake a proof-of-concept feasibility study for using biomarker results to determine management. Children in this Aim will be recruited from the cohort of children in Aim 2, and therefore

will have all the tests carried out at the same intervals. If parents consent to taking part, children will have the following treatment adjustments based on the results of their tests (Table 5):

Table 5: Proposed biomarker guided management for proof-of-concept feasibility study

Biomarker result at baseline assessment	Treatment
Allergen sensitisation +/- blood eosinophilia ($\geq 0.3 \times 10^9/L$)	Regular inhaled corticosteroids
Non-atopic*; positive bacterial detection in sputum	4 weeks of targeted antibiotics
Non-atopic*; negative bacterial infection	Short acting bronchodilators as required

*non-atopic is defined as blood eosinophil of $<0.3 \times 10^9/L$ + no evidence of allergen sensitisation

This proof-of-concept study will be undertaken to understand whether parents will agree to their children taking part in an interventional trial, and to assess the feasibility of the proposed targeted treatment approach in a subgroup of wheezers. Wheeze attacks and symptoms over the course of a year will be compared to the children in Aim 2 as a reference control cohort. This aim will enable a more accurate sample size calculation and design for a future interventional trial.

The sputum samples, oropharyngeal swabs and finger prick blood test will be collected by a clinical research fellow or research nurse. Bronchoscopy samples (bronchoalveolar lavage and endobronchial biopsy) will be collected by a clinician responsible for the patient, as part of the samples collected for the patient's clinical management and surplus samples will be used for this study, with parental consent.

In all three aims, **parents and the child can refuse any test at any visit** and continue to take part in this study. This will be made very clear at recruitment and during each study visit. One of our key aims is to look at the acceptability of the proposed non-invasive tests to both parents and the child, and therefore, the reason for refusal will be recorded. This will help us understand the acceptability of particular tests and the frequency of testing that is deemed acceptable. We will also perform a visual analogue score for every test done on the child to assess tolerance and acceptability.

The participants will have a thorough respiratory assessment (including lung function tests, skin prick allergy testing) and the results will be made available immediately to the participants and caregivers, as part of the study. Incidental findings, during the course of the assessment, would be communicated to the families, and their GP and clinical care team - examples may include incidental bacterial infection, for which the participants will be prescribed appropriate treatment.

In some cases, children may have an incidental finding during the study, such as identified as having respiratory disease or symptoms that require further referral or treatment, and in such cases their families and their usual health care providers (GP and clinical care team) will be informed.

End of study is defined as last research visit of the last subject recruited.

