Aim 1: Children participating in this aim are recruited from the cohort of preschool wheezers who have been identified by their existing clinical teams as needing a bronchoscopy, as part of their standard clinical management. We will aim to use surplus samples taken during the bronchoscopy and endobronchial biopsy for the study, with parental consent. Number of children: 50.

Aim 2: Children participating in this aim are recruited from the respiratory clinics who meet the criteria listed below. Children recruited for Aim 1 can be recruited into Aim 2. Number of children: 100

Aim 3: Children participating in this aim can be recruited from Aims 1 or 2, as this is a small proof-of-concept study to investigate biomarker-driven targeted therapy for preschool wheeze. Number of children: 15

Duration:

Over 36 months, with each child being followed-up for 12 months after recruitment.

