Information related to the feasibility of the intervention will be gathered using a combination of quantitative and qualitative methods. Descriptive statistics will be used to summarise the baseline demographics of all patients included in the feasibility analysis and to evaluate parental and children's satisfaction with the various diagnostic tests. To identify factors responsible for dropout, baseline characteristics and questionnaire scores of patients who agreed or did not agree to undergo follow-up will be compared using parametric and non-parametric tests, where appropriate.

To understand the robustness of the proposed diagnostic approach, I will investigate the temporal variation in biomarker trajectories and their relation to clinical status by adopting longitudinal generalised linear models and dynamic Bayesian networks (dBNs). Bayesian networks (BN) are probabilistic graphical models that, using Bayes' theorem, represent knowledge about a certain domain/disease by encoding conditional dependences among random variables in directed acyclic

graphs. A dBN is the extension of a BN applied to longitudinal data. The model describes the dependencies among the variables over time. This allows for encoding cycles and feedbacks between variables to represent their relationships over different time windows. The heterogeneity of the joint dynamics of wheeze recurrence and biomarker variation will be explored using joint latent class models for recurrent events, which will allow me to identify subgroups of children characterised by different disease risk profiles linked to specific biomarker variations. The groups are formed to minimise the within-class variability both with respect to the evolution of longitudinal markers and to the occurrence of an event.

To identify differences between patients in the intervention study compared to those in the observational arm, I will perform differential longitudinal analysis. I will combine simple parametric and nonparametric hypothesis testing techniques with time-varying models based on time-series analysis and smoothing splines. Symptom scores will be recorded using a validated questionnaire at each visit for those in the intervention study and adjustments will be made for season.

Data and all appropriate documentation will be stored for a minimum of 10 years after the completion of the study, including the follow-up period.

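### The planned Aim 3 v Aim 2 tests of attacks and symptoms name season as the only adjustment, although children enter Aim 3 by parental consent

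*Combined protocol and SAP*

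**What the plan says.** Section 6 sets up Aim 3 as a proof-of-concept feasibility study. Children whose parents consent have treatment guided by their baseline biomarkers. It then plans an outcome comparison: "Wheeze attacks and symptoms over the course of a year will be compared to the children in Aim 2 as a reference control cohort".

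Section 7 (Data Analysis, Aims 2 and 3) gives the method: "To identify differences between patients in the intervention study compared to those in the observational arm, I will perform differential longitudinal analysis". It continues: "I will combine simple parametric and nonparametric hypothesis testing techniques with time-varying models based on time-series analysis and smoothing splines". The one adjustment named is in the next sentence, on symptom scores, which are to be recorded "at each visit for those in the intervention study and adjustments will be made for season".

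On membership of the groups, section 3 says: "Children participating in this aim can be recruited from Aims 1 or 2". Section 6 says: "Children in this Aim will be recruited from the cohort of children in Aim 2". The targets are 15 children in Aim 3 and about 100 in Aim 2.

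Table 4 schedules TRACK, skin prick testing and finger-prick blood at baseline for both groups. Medical history is taken at every visit.

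**The concern.** Entry to Aim 3 depends on a parental decision. Section 6 expects many parents to hesitate over treatment changes, and section 7 reports that 20% of families agreed to a previous interventional trial. Families who agree may therefore differ from the rest in ways related to later attacks or symptoms.

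The plan names no baseline covariate, matching or weighting for this contrast. The longitudinal models include the baseline visit, so they would show a gap in baseline TRACK, but showing a gap does not control for it. For attacks no baseline measure is named, and it is unclear whether the season adjustment applies to them, because it stands in a sentence on symptom scores.

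What is at stake is narrow: a p-value from this contrast could be taken as evidence that biomarker-guided care works or does not. Section 6 also says that Aim 3 will inform the sample size and design of a future trial. Section 7 ties that to uptake and reasons for declining, but nothing stops a confounded difference from being used as well.

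**Working it through.** **1. The plan's own figure.** There is none for this contrast. The power statement for Aim 3 in section 7 concerns agreement and sensitivity, not a difference between groups, so there is nothing to reproduce.

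**2. Group sizes.** Aim 3: 15. Comparator: 100 − 15 = 85 if all 15 come from Aim 2 and are removed; 100 if they stay in or come from outside Aim 2.

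**3. Precision of an unadjusted mean difference, in SD units.**
- 15 v 85: SE = √(1/15 + 1/85) = 0.280; 95% half-width = 1.96 × 0.280 = 0.549.
- 15 v 100: SE = 0.277; half-width 0.543.

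**4. Illustration of selection (all inputs assumed).** Let baseline severity Z be standard normal, with logit P(consent) = a + ln(OR) × Z and mean P = 15/100 = 0.15. Let d be the resulting mean difference in Z between consenters and others, and r the correlation of Z with the outcome. With no treatment effect, the bias of the unadjusted difference is r × d. A two-sided 5% test then rejects with probability Φ(−1.96 + bias/0.280) + Φ(−1.96 − bias/0.280).

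| OR per SD | d | r | Bias (SD) | Rejection |
|---|---|---|---|---|
| 1.0 | 0 | any | 0 | 5.0% |
| 1.25 | 0.222 | 0.3 | 0.067 | 5.6% |
| 1.5 | 0.397 | 0.5 | 0.199 | 10.9% |
| 2.0 | 0.652 | 0.6 | 0.391 | 28.7% |

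With only one input at its extreme the figure is much lower: 10.7% for OR 2.0 with r 0.3, and 7.6% for OR 1.25 with r 0.6. If uptake were 20%, the top case would be 34.0% for 20 v 80 (0.20 × 100 = 20) or 26.8% for 15 v 60 (15/0.20 = 75). Neither is the planned configuration.

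**5. The same cases after adjustment.** Adjust for a baseline measure of Z with reliability R. Approximately, bias = (1 − R) × r × d and SE = 0.280 × √(1 − R × r²).
- R = 1: bias 0, rejection 5.0%, half-width 0.524 (r = 0.3) to 0.439 (r = 0.6).
- R = 0.7: bias 0.020, 0.060 and 0.117; SE 0.271, 0.254 and 0.242; rejection 5.1%, 5.6% and 7.7%; half-width 0.531 to 0.475. A simulation of the top case (6,000 runs, 15 of 100 selected, linear model) gave 8.2%.

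This holds only if selection acts through the baseline measure that is adjusted for.

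**6. Overlap.** If all 15 stayed in a comparator of 100, the estimated difference would be T − (0.15T + 0.85C) = 0.85(T − C), that is 85% of its size.

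**7. Source of Aim 3 children.** Section 3 allows entry from Aims 1 or 2; section 6 names Aim 2. The distinction matters because Aim 1 is a "One-off assessment carried out on the day of the bronchoscopy and no follow-up needed" in children having bronchoscopy for severe wheeze. A child entering Aim 3 directly from Aim 1 would not come from the reference cohort.

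**The case against.** The strongest reply is that little depends on this contrast. Aim 3 asks whether parents will agree to take part, and sections 3 and 3.1 do not make the contrast an outcome in its own right. That is right, and it makes this an improvement and not a flaw in the main aim. It does not remove the point, because section 7 still plans hypothesis tests.

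The illustration can also be challenged. It ties consent to severity, whereas the documents speak of hesitancy and adherence. It models a continuous score, although the absence of a baseline measure is plainest for attacks, which are counts. Even its largest bias (0.39 SD) is smaller than the 95% half-width (0.55 SD). All of this stands. The figures show what an unadjusted test could do and do not estimate what it will do. If selection works through attitude or adherence, baseline TRACK need not capture it. Nor would adjustment fully isolate biomarker-guided care: under section 6 all participants receive their results, and incidental bacterial infection is treated.

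A reader might infer that the 15 children are counted on both sides, or that sections 3 and 6 contradict each other outright. The documents do not support either. The phrase observational arm in section 7 implies separate groups, and section 3 lets Aim 1 children join Aim 2, so they can reach Aim 3 through it. What remains is a matter of wording.

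Section 7 does compare baseline data of those who "baseline characteristics and questionnaire scores of patients who agreed or did not agree to undergo follow-up will be compared" (the last words of the quote complete the clause), but this concerns dropout and does not bear on consent to Aim 3.

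**Conclusion.** The point holds in limited form and should be addressed. A non-randomised contrast of about 15 children is to be tested with season as the only named adjustment, although baseline TRACK and atopic status are available at no extra cost. This conclusion rests on the text and does not depend on the illustration.

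The size is unknown. With assumed odds of consent of 1.25 to 2.0 per SD of severity and an assumed correlation of 0.3 to 0.6, false rejection is about 6% to 29% for an unadjusted 15 v 85 test of a continuous score, which is one component of the planned analysis. With adjustment at reliability 0.7 to 1 it is about 5% to 8%, if selection acts through that baseline.

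Two stronger readings are tempting and should be resisted. One is that consenting families are known to have sicker children: no passage links consent to severity, and the shared entry criteria in section 4.2 may limit any difference. The other is that Aim 3 is invalidated: its findings on willingness and feasibility do not depend on this contrast.

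**What to change.** In section 7:

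- **Symptoms:** adjust for baseline TRACK and baseline atopic status, and keep season.
- **Attacks:** adjust for atopic status and, if medical history or eligibility screening records a count, prior-year admissions. Section 4.2 uses admissions only as an entry threshold, so first confirm that a count exists.
- **No further covariates:** 15 children support few.
- **Reporting:** replace the tests by estimates with 95% CIs, labelled exploratory, and state that adjustment does not remove selection through parental attitude or adherence.

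As a clarification in sections 6 and 7, state that the comparator is Aim 2 children not enrolled in Aim 3. Reconcile sections 3 and 6 on where Aim 3 children come from.

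The cost is some wording, a little more analysis and giving up p-values for this contrast. No new visits, tests or participants are needed.
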